2.1.1 General definitions

Study drug is defined as any single dose of TIP or placebo administered to the patient as part of the required study procedures.

The date of first dose of study drug is defined as the date of first administration of TIP or placebo; the date of last dose of study drug is defined as the date of the last administration of TIP or placebo.

For dates on or after the date of first dose of study drug, study day is defined as [date of interest – date of first dose of study drug] + 1. For dates before the date of first dose of study drug, study day is defined as [date of first study drug – date of interest].

For each visit, the date recorded by the investigators in the eCRF (variable SVSTDTC in the SDTM SV dataset) will be considered as the visit date in all the algorithms and the listings.

In general, the nominal visits will be used for the by visits summaries. However, for early treatment discontinued patients, data collected at end of treatment (EOT) visit will be mapped to next planned visits after their last scheduled visits before the discontinuation.

Baseline is defined as the last non-missing result prior to the first administration of study drug.

End/last date of study for each patient is defined by the date of last contact as recorded in the database.

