2.4 Treatments (study treatment, rescue medication, concomitant therapies, compliance)

2.4.1 Study treatment / compliance

Overall exposure (days) to study treatment will be summarized in terms of treatment duration, defined as the number of days from the date of first dose of study drug taken to the date of the last dose of study drug taken, inclusive, i.e., date of last dose of study drug – date of first dose of study drug + 1.

Assessment of compliance will be based on the number of unused capsules returned per patient assessed by the Independent Study Coordinators (ISC).

Compliance will be derived using the following formula:

Compliance = (number of actual inhaled capsules / number of intended inhaled capsules during the derived treatment period) * 100%

The number of intended inhaled capsules during the treatment period will be derived as follows:

- Cohort A: 3 * treatment duration
- Cohort B: 5 * treatment duration
- Cohort C: 8 * treatment duration

Compliance will also be assessed by visit period. Four specific periods will be defined, i.e., Visit 101 to Visit 103, Visit 103 to Visit 104, Visit 104 to Visit 105, and Visit 105 to Visit 106. This will be used to review the compliance for each on/off active treatment period for the cyclical TIP/placebo treatment arms.

Descriptive statistics (n, mean, SD, minimum, median, and maximum) will be presented by cohort and treatment arm for the FAS for overall exposure, and both compliance over the treatment period and compliance by visit period. Duration of exposure will be further categorized as ≤ 22 days, 23-28 days, 29-56 days, 57-84 days, 85-112 days, ≥ 113 days, and the number and percentage of patients by cohort and treatment arm will be presented for each category for the FAS.

The number and percentage of patients with study drug compliance $< 80\%$ and $\geq 80\%$ over the treatment period and for each visit period will also be summarized by cohort and treatment arm using the FAS.

Overall duration of study (days), defined as the number of days from the date of randomization to the date of study completion, i.e., date of study completion – date of randomization + 1, will be summarized descriptively (n, mean, SD, minimum, median, and maximum) by cohort and treatment arm for the FAS.

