2.6 Analysis of secondary and exploratory efficacy objective(s)

For efficacy analysis, patients assigned to placebo arms will be pooled across the 3 cohorts, as the number of placebo capsules is not expected to impact the efficacy assessments. Unless otherwise specified, the following analysis will be conducted both over the treatment epoch (through Day 113) and over the entire study period (through Day 169).

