The time to first pulmonary exacerbation overall will be analyzed using a Cox regression model stratified by baseline macrolide use. The model will include treatment as a fixed-effect factor, and number of pulmonary exacerbations in the 12 months prior to screening as a covariate. Six pairwise comparisons will be evaluated as specified in [Section 2.6.3](#), in addition two pairwise comparisons will be evaluated between pooled continuous regimens vs pooled placebo and, between pooled cyclic regimens and pooled placebo. The estimated adjusted hazard ratio for TIP over placebo will be displayed along with the associated 2-sided 95% CI. For analyses conducted across the treatment period, patients will be censored at the time of last dose of study drug if they did not have a pulmonary exacerbation during the treatment period. Similarly, for analyses conducted across the study period, patients will be censored at the time of last contact if they did not have a pulmonary exacerbation during the study period.

Kaplan-Meier analysis stratified by cohort and treatment arm and by pooled arms (continuous and alternating regimens) will be also presented and displayed graphically.

The time to first pulmonary exacerbation requiring parenteral antibiotics or hospitalization, and the time to first pulmonary exacerbation requiring hospitalization will also be analyzed using the same approach as described for the time to first pulmonary exacerbation overall.

The exposure adjusted rate of pulmonary exacerbations overall

The exposure adjusted rate of exacerbations will be determined across the treatment period and will be derived as follows:

(Number of pulmonary exacerbations reported during the treatment period / sum of exposure time during the treatment period for all patients during the treatment period) / 365.25

The number of pulmonary exacerbations during the treatment period will be analyzed using a generalized linear model assuming the negative binomial distribution including treatment and baseline macrolide use as fixed-effect factors, and number of pulmonary exacerbations in the 12 months prior to screening as a covariate. The log exposure to treatment in years will be included as an offset variable in the model.

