2.6.3.4 Hospitalization

Proportion of patients requiring hospitalization due to serious respiratory-related AEs

The proportion of patients requiring hospitalization due to serious respiratory-related AEs across the treatment period, follow up period, and across the entire study period will be summarized by treatment arm and by pooled continuous and cyclic regimen. The number of events will also be summarized.

The time to first hospitalization due to serious respiratory-related AEs

The time to first hospitalization due to serious respiratory related AEs will be analyzed using a Cox regression model stratified by baseline macrolide use. The model will include treatment as a fixed-effect factor, and number of pulmonary exacerbations in the 12 months prior to screening as covariate. Six pairwise comparisons will be evaluated as specified in [Section 2.6.3](#), in addition two pairwise comparisons will be evaluated between pooled continuous regimens vs pooled placebo and, between pooled cyclic regimens and pooled placebo. The estimated adjusted hazard ratio for TIP over placebo will be displayed along with the associated 2-sided 95% CI.

Kaplan-Meier analysis stratified by treatment arm will be also presented and displayed graphically.

If a small number of events occur after pooling events, only the Kaplan-Meier estimation of time to first hospitalization due to serious respiratory-related AEs will be provided.

Duration of hospitalization due to serious respiratory-related AEs

The duration of hospitalization due to serious respiratory-related AEs (days) across the entire study period will be summarized by treatment arm [and](#) pooled arms by continuous and cyclic regimens. Summaries will be event driven and not patient driven.

Number of hospitalizations due to serious respiratory-related AEs

The number and percentage of patients with 0, 1, 2, >2 hospitalizations due to serious respiratory-related AEs across the entire study period will be summarized by treatment arm

[figure not shown]
and pooled arms by continuous and cyclic regimens.

The exposure adjusted rate of hospitalization due to serious respiratory-related AEs

The exposure adjusted rate of hospitalization due to serious respiratory-related AEs will be determined across the study period.

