The number of hospitalization due to serious respiratory-related AEs during the study period will be analyzed using a generalized linear model assuming the negative binomial distribution including treatment and baseline macrolide use as fixed-effect factors, and number of pulmonary exacerbations in the 12 months prior to screening as a covariate. The log exposure to treatment in years will be included as an offset variable in the model.

Six pairwise comparisons will be evaluated as specified in [Section 2.6.3](#), in addition two pairwise comparisons will be evaluated between pooled continuous regimens vs pooled placebo and, between pooled cyclic regimens and pooled placebo. The estimated rate ratio along with 2-sided 95% interval will be provided.

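### SAP 2.6.3.4 counts respiratory hospitalizations over the whole study period but offsets the rate model by time on treatment, so follow-up is in the count and not in the time at risk

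*SAP*

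**What the plan says.** In SAP 2.6.3.4 the count and its window are: "The number of hospitalization due to serious respiratory-related AEs during the study period will be analyzed using a generalized linear model". The offset is: "The log exposure to treatment in years will be included as an offset variable in the model". The output is: "The estimated rate ratio along with 2-sided 95% interval will be provided". Just before the model, the same section adds: "The exposure adjusted rate of hospitalization due to serious respiratory-related AEs will be determined across the study period". It names no denominator for that rate.

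The time definitions are elsewhere:

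- SAP 2.6 takes the study period through Day 169.
- SAP 2.4.1 defines overall exposure as "the number of days from the date of first dose of study drug taken to the date of the last dose", inclusive. SAP 2.1.1 adds: "Study drug is defined as any single dose of TIP or placebo administered to the patient".
- Protocol 5.5.4 places the last administration on the morning of Day 113.
- Protocol Table 6-1 has respiratory hospitalizations recorded at both follow-up visits. Protocol 5.6.2 sends patients who stop drug early into a two-month follow-up.

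The protocol does not choose an offset. Its section 9.5.1.4 refers hospitalization to the exacerbation models, and the offset in 9.5.1.2 is log exposure in years, not tied to a window.

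**The concern.** In a count model with a log offset, the offset should be the time during which the counted events could occur. Here a completer can contribute events for 169 days but is credited with 113. A patient who stops early and is then followed is credited with even less of the time actually at risk.

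Two results could be affected. The rate ratio, which also feeds a forest plot in SAP 2.6.3, would shift if the arms differ in how many patients stop, when they stop, or how long they are followed afterwards. Tolerability of the powder in this population is one of the trial's own questions (Protocol 3.2), so equal stopping cannot be taken for granted. Any absolute hospitalization rate on this denominator would be too high in every arm.

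**Working it through.** **Comparison of the SAP's count models**

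| SAP section | Events counted over | Offset |
|---|---|---|
| 2.6.3.2, exacerbations | treatment period | log exposure to treatment |
| 2.6.3.2, exacerbations | entire study period | log time in study |
| 2.6.3.3, anti-pseudomonal antibiotics | entire study period | log time in study |
| 2.6.3.4, respiratory hospitalizations | study period | log exposure to treatment |

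Only the last row is mismatched. Its offset sentence repeats the one in the first row, where it fits because of the count it accompanies: "The number of pulmonary exacerbations during the treatment period will be analyzed using a generalized linear model". SAP 2.6.1.4 (endpoint list), 2.6.3 (forest plot) and 2.6.3.4 (rate) all place hospitalization over the study period. SAP 2.6.4 deals only with censoring in time-to-event analyses, so it does not resolve the conflict.

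**Size of the effect**

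The plan states no hospitalization rate or event count, so there is no figure of its own to reproduce.

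Inputs from the documents: 113 exposure days and 169 study days for a completer; 56 days of follow-up; about 20% discontinuation (Protocol 9.7).

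Assumptions: a constant event rate, and stopping unrelated to events. Stop days are uniform over Days 1–112 (mean 56.5) or, as an early-stopping case, over Days 1–56 (mean 28.5). The splits of stopping between arms are also assumed, because the documents give only the overall figure.

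With proportion p stopping at mean day m and mean study time S for stoppers, the factor by which a rate is overstated is

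F(p) = [(1 − p)·169 + p·S] / [(1 − p)·113 + p·m]

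where S = m + 56 (the Protocol 5.6.2 path), S = m (stoppers leave) or S = 169 (followed to Day 169). The apparent rate ratio with no true effect is F(p on TIP) / F(p on placebo).

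- Completers: 169/113 = 1.50.
- 20% stopping, 56-day follow-up: (0.8×169 + 0.2×112.5) / (0.8×113 + 0.2×56.5) = 157.7/101.7 = 1.55.
- 30% on TIP vs 10% on placebo, 56-day follow-up: (152.05/96.05) / (163.35/107.35) = 1.583/1.522 = 1.04.
- The same split, stoppers leave: (135.25/96.05) / (157.75/107.35) = 1.408/1.469 = 0.96.

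| Stoppers are | F at 20% | Null ratio, 30% vs 10% | Null ratio, 25% vs 15% |
|---|---|---|---|
| followed 56 days | 1.55 (1.58) | 1.04 (1.07) | 1.02 (1.03) |
| gone at stop | 1.44 (1.47) | 0.96 (0.98) | 0.98 (0.99) |
| followed to Day 169 | 1.66 (1.76) | 1.12 (1.19) | 1.06 (1.09) |

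Brackets give the early-stopping case. With equal stopping and follow-up every null ratio is 1.00.

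Two simulations support the arithmetic:

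- A large simulated negative binomial fit (assumed 0.5 events/year, dispersion 1, all stops at Day 29, 30% vs 10%, 56-day follow-up) gave a null ratio of 1.08, against 1.07 by person-time. With time in study as the offset it returned to 1.00.
- When hospitalization itself triggered stopping (assumed probability 0.25–0.5, 0.3–1.0 events/year), the factor was 1.50–1.53 and a true ratio of 0.50 moved by under 2%.

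**Precision for comparison**

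With 107 randomized (SAP 1), the planned allocation gives 107×2/15 = 14.3 per active arm, 107×6/15 = 42.8 per pooled regimen and 107×3/15 = 21.4 on pooled placebo. At an assumed 0.6 events/year over 169 days:

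- Single arm vs placebo: 4.0 vs 5.9 events. The 95% limits lie a factor exp(1.96·√(1/4.0 + 1/5.9)) = 3.6 either side.
- Pooled regimen vs placebo: 11.9 vs 5.9 events, factor 2.7.

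Over 1.0 down to 0.2 events/year the factors run from 2.7 to 9.0 and from 2.1 to 5.5. These are Poisson figures; overdispersion would widen them.

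**The case against.** The best defence is that little depends on this. The analysis is secondary and unadjusted for multiplicity, and SAP 1 treats all inference as exploratory after early closure. The specified output is a ratio, in which a common understatement of time at risk cancels. The unequal stopping splits are assumptions, and the larger shifts of 1.12–1.19 need stoppers to be followed to Day 169 rather than for the two months in Protocol 5.6.2. The intent can also be recovered: Protocol 9.5.1.4 points to the exacerbation models, and the SAP's study-period version of that model uses time in study. All of this stands and limits the weight of the point. It does not make the sentence right: a programmer must either fit a mismatched model or depart from the SAP.

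A reader might infer that the cyclical arms are badly distorted, because Protocol 9.3 sums their exposure over two treatment cycles and that could be taken as active-drug days only. The documents do not support this. Protocol 3.3 and 5.2 and SAP 1.1 describe each cycle as 28 days of TIP followed by 28 of placebo, 112 days in all. SAP 2.4.1 with 2.1.1 counts TIP and placebo doses alike. Exposure in those arms is therefore about the same as elsewhere.

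**Conclusion.** The offset in SAP 2.6.3.4 is wrong as written and should be corrected. It does not match the window of its own count, and it departs from the SAP's convention for study-period counts.

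The effect on the rate ratio is nil with equal stopping and follow-up. It is about 2–7% under the assumed unequal splits with 56 days of follow-up, and 1–4% in the other direction if stoppers leave. These figures rest on a constant event rate and the assumed stop days. They are minor beside the imprecision expected with 107 patients, and the primary analysis is untouched.

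Two stronger conclusions should be avoided. One is that the reported hospitalization rates will be about 50% too high. The model promises only a rate ratio, and the separate rate is described as running across the study period with no denominator named. The 1.50-fold figure (1.55 at 20% stopping) applies only if a model-based rate is reported or that separate rate borrows the model's denominator. If it used study time instead, the rate and the ratio in one section would rest on different time bases. The other is that the error works against TIP. The direction depends on which arm stops more and on how stoppers are followed, and the documents establish neither.

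**What to change.** In SAP 2.6.3.4, replace the offset with the log of years in study, as in the study-period model of 2.6.3.2 and in 2.6.3.3. State that the exposure-adjusted hospitalization rate in the same section divides the number of events by total time in study. The study-period formula in 2.6.3.2 can supply the denominator but not the numerator, which there counts patients rather than events.

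If an on-treatment rate is also wanted, add it as a separate model with the count restricted to the treatment period. Keep the exposure offset for that model only, and refer to the definition in SAP 2.4.1.

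The cost is one or two lines of text. Time in study is already needed for the exacerbation and antibiotic models, so there is no new derivation.

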2.6.4 Handling of missing values/censoring/discontinuations

For time to event analyses, patients not experiencing that event will be censored at either the time of last dose of study drug (if the analysis is across the treatment period) or the date of last follow-up visit (if the analysis is across the entire study period).

2.7 Safety analyses

All safety analyses will be performed using the SAF, and will be presented by cohort and treatment arm (TIP, TIP/placebo cyclical, placebo and pooled placebo).

Baseline for safety analyses is defined as the last measurement prior to the first dose of study drug in the study.

Appropriate summary statistics will be provided for laboratory test results, audiology, bronchial hyperreactivity and vital signs.

Safety data will be presented in the individual patient data listings based on the SAF. Only descriptive analysis of safety will be performed (i.e., no statistical hypothesis testing will be performed).

Table 2-2 shows the safety parameters (e.g., raw value, change from baseline, incidence, and clinical abnormalities) that will be summarized for AEs/Serious AEs (SAEs), laboratory data (serum chemistry/hematology, urinalysis), 12-lead ECG and vital signs.

For the non-AE safety evaluations, raw values, and changes from baseline will be summarized as indicated in Table 2-2. For example, an “X” under the raw value column (second column) means that the raw values for the safety evaluation will be summarized; an “X” under the change column (third column) means that change will be summarized.

Throughout this section, “change” refers to absolute change from baseline.

Table 2-2 Summaries of safety data

Safety Assessment	Incidence	Raw Value	Change	Clinical Abnormalities
AEs*	X			Not applicable
Serum Chemistry/Hematology		X	X	X
Urinalysis	X	X	X	X
12-lead ECG		Present in listing only		
Vital signs		X	X	Not applicable

ECG: electrocardiogram; X: safety assessment will be summarized in tables.

*AEs, SAEs and other significant AEs or AEs of special interest, see Section 2.7.1

2.7.1 Adverse events (AEs)

An AE will be classified as a treatment emergent AE (TEAE) if it starts on or after the date of the first dose of study drug until study completion.

TEAEs will be summarized by System Organ Class (SOC) and Preferred Term (PT) using the latest Medical Dictionary for Drug Regulatory Affairs (MedDRA) available at the time of database lock.

The number and percentage of patients experiencing TEAEs, SAEs, AEs suspected to be related to study drug, AEs leading to study drug discontinuation and AEs leading to death will be summarized by treatment arm and overall.

The number and percentage of patients experiencing TEAEs will be summarized by treatment arm by SOC and PT, and by SOC, PT and maximum severity. In addition, the number and percentage of patients experiencing AEs suspected to be related to study drug will be summarized by treatment arm by SOC and PT.

For the legal requirements of ClinicalTrials.gov and EudraCT, two required tables on TEAEs which are not serious adverse events with an incidence greater than 5% and on treatment emergent SAEs and SAEs suspected to be related to study treatment will be provided by SOC and PT using the SAF.

If for the same patient, several consecutive AEs (irrespective of study treatment causality, seriousness and severity) occurred with the same SOC and PT:

- a single occurrence will be counted if there is ≤ 1 day gap between the end date of the preceding AE and the start date of the consecutive AE
- more than one occurrence will be counted if there is > 1 day gap between the end date of the preceding AE and the start date of the consecutive AE

For occurrence, the presence of at least one SAE / SAE suspected to be related to study treatment / non SAE has to be checked in a block e.g., among AEs in a ≤ 1 day gap block, if at least one SAE is occurring, then one occurrence is calculated for that SAE.

The number of deaths resulting from SAEs suspected to be related to study treatment and SAEs irrespective of study treatment relationship will be provided by SOC and PT.

AEs of special interest (AESIs):

The number and percentage of patients with AEs regarding ototoxicity and/or hemoptysis and renal events will be summarized. Specific AE terms will be collected on the AESI electronic case report forms (eCRFs). These data include symptoms, medical history and relevant local assessment.

In addition, post-inhalational adverse events will be summarized as instructed 2.7.4.3.

